## **12.8 Case Report Form**

The database programmer of CRO will establish eCRF in the Clinflash system. Different subjects are identified on the eCRF only by appropriate identification codes (e.g., site No. and subject number). The eCRFs are used for the documentation of clinical study data of subjects, and are a component of this study and relevant study reports. Entry must be therefore accurate and complete. The eCRFs are entered into Clinflash system by the investigator or personnel authorized by the investigators (indicated in the study authorization table). It must be ensured that all data entry is completed and stored. The investigator must state that all information in eCRF is true by electronic signature.

In clinical study, eCRF should be completed as soon as possible after each visit to record the condition of subjects.

The medical records and other records related to disease progression of subjects during the study period will be stored by the investigators. These records should contain the following contents: original or copy of laboratory data and other medical test results (e.g., 12-lead ECG, etc.). These materials must be stored at the site with subjects' medical records.

## **12.9 Monitoring**

Monitoring will be conducted by the sponsor or its commissioned CRO.

Before certain study site is selected to participate in this study, one site selection visit will be performed to confirm that such site, equipment and site personnel meet protocol requirements and GCP.

During the study period, the monitors should routinely perform on-site monitoring. At each monitoring, visit date will be documented at site visit records of the study sites. The sponsor shall determine whether to perform site monitoring based on the quality of the study.

**CRA's study monitoring activities include:**

- Perform study initiation visit to the study site, collect and distribute necessary documents before study; provide guidance and description of the protocol, study procedure and expectation to investigators and site staff; obtain investigators' guarantee of conducting the trial in compliance with study requirements and the GCP and introduce study materials to investigators and corresponding study staff.
- Monitoring visit: According to the requirements of GCP, CRAs taking part in the current study should completely understand affairs of confidentiality and compare the data in the eCRF with those in the hospital or clinical record (source documents). Before the initiation of the study, the CRA should discuss the specific items required as source documents with the investigator and confirm the nature and storage place of all source documents, so as to guarantee that the sponsor or the investigator could know the origin of source data for eCRF completion, and the CRA authorized by the sponsor has the right to check and verify the data. All observations and findings during the monitoring process must be verified. If the electronic records are stored at study institutions, the verification methods must be discussed with the study personnel.

**Source documents must be available for confirming:**

- The identity of subject, whether the subjects are qualified and participate the study or not;
- Appropriate informed consent procedure;
- Visit date;
- Records of safety and efficacy parameters;
- Sufficient reports and visits of AEs;
- Treatment with concomitant medications;

- Records of receipt/dispensing/return of drugs;
- Administration information of investigational product;
- Subjects' completion of treatment, termination of treatment or withdrawal from the study and appropriate reasons;
- The data are authentic, accurate and complete;
- Subjects' safety and rights are protected;
- Investigator's implementation complies with the currently approved protocol, GCP and all relevant regulatory requirements.

**Objectives that the monitoring should realize include:**

- Check and assess the trial progress;
- Review the collected trial data;
- Carry out verification of source documents;
- Identify any problems and develop solutions.

During the study period, CRAs are required to directly review all related documents with the consent of the investigator. The investigators should ensure that they and relevant study personnel should regularly meet with CRAs to discuss findings during monitoring visits and related issues.

**12.10 Intellectual Property**

All study materials on study drug, such as patent application, dosage form, manufacturing process, basic research, etc., are considered confidential as long as they are not published. All information obtained from the trial sponsor and the trial belongs to the intellectual property rights of the trial sponsor. Therefore, all relevant personnel of the clinical trial must strictly keep it confidential, and should not disclose it to any third party without the prior consent of the sponsor. It should not be used for other purposes other than the study.

**12.11 Subject's Privacy**

Study personnel must ensure to protect privacy of subjects in the clinical trial. In all eCRFs, documents and files submitted to sponsor, the clinical trial subjects can only be identified by clinical trial screening number. Full name of a subject is never indicated. The investigator must store the private information, e.g., name and address, of the subjects in the clinical trial

in a strictly confidential manner, and may not submit it to the sponsor.

### **13 Paper Publications**

The study data and manuscript obtained in this study will also be considered confidential. Hangzhou Phecdamed Co., Ltd., as the sponsor, has the exclusive right to this trial and has the right to decide to disclose it to other clinical study staffs and national regulatory agencies. Authors and the manuscript will reflect coordination between investigators and study sites and staff of the Sponsor. Authors will be identified before drafting of the manuscript. Many study sites are participating in this study, unless prior consent has been obtained from the Sponsor, individual shall not publish any data related to the clinical study before the final report of the multi-center study has been completed. The sponsor has the right of final decision about the manuscript and publication.

## **14 Clinical Data Archiving**

### **14.1 Source Data and Source Documents**

In this trial, source data includes records on the clinical findings, observations, and other activities required to reconstruct and evaluate the clinical trial. The original data is contained in the source files.

The source files involved in the clinical study are original records, documents and data (such as hospital medical records, medical images, laboratory records, memos, subject diaries or assessment forms, drug distribution records, data automatically recorded by instruments, subject files, clinical trial-related documents and records kept by pharmacies, laboratories, and medical technology departments, including certified copies, etc.). Source documents must be retained to support the information provided in eCRFs.

### **14.2 Data Archiving of Study Site**

#### **14.2.1 Materials related to the Ethics Committee**

Personnel responsible for data storage at the study site must keep records and synopsis of EC meetings till 5 years after termination or completion of the study. If the sponsor wishes to retain for a longer period, the two parties will discuss and decide the retention duration and methods. If the study site makes any changes in document retention, personnel or investigator responsible for document retention should contact the sponsor.

#### **14.2.2 Materials related to Trial Conduct**

The personnel in charge of materials preservation in the study site must keep the following files until 5 years after the investigational drug is approved for marketing. If the sponsor wishes to retain for a longer period, the two parties will discuss and decide the retention duration and methods. If the study site makes any changes in document retention, personnel or investigator responsible for document retention should contact the Sponsor.

- Original materials;
- Trial contract, original copy or copies of the ICF, other GCP-related materials provided by the site staff;
- Study protocol, GCP-related materials obtained from the EC, or other GCP-related materials obtained;

- Records of management of the investigational product and other records related to trial conduct.

#### **14.3 Data Archiving of Sponsor**

The sponsor will store the following materials (including documents and data) until 5 years after the investigational drug is approved to be marketed. A longer retention period may be required according to relevant regulations. It is the responsibility of sponsor to inform the investigator/study site as to when such data is no longer required to be retained:

- Study protocol, trial agreement, the original or duplicate copies of the study reports, or GCP-related materials provided by the sponsor;
- Case report form, GCP-related notifications, or GCP-related materials obtained from the investigators;
- Monitoring and audit records, or other relevant operation records;
- Data obtained in the trial;
- Relevant records specified in GCP.

## 15 Protocol Amendments

After this protocol has been approved by the Ethics Committee, if any modifications should be made, the protocol amendment statement should be drafted and signed by the principal investigator. Protocol amendment is allowed after the approval of the sponsor. Protocol amendment can be implemented after being reviewed or archived by the EC.

Protocol/Amendment	Version	Formulation Date	Revised Content
TJJS01-201	V1.0	August 19, 2024	Initial version
TJJS01-201	V2.0	September 24, 2024	See corresponding amendment record
TJJS01-201	V3.0	December 20, 2024	See corresponding
TJJS01-201	V4.0	February 17, 2025	See corresponding

## 17 Appendices

### 17.1 Appendix I: Definition of Women of Childbearing Potential and Contraceptive Requirements for Subjects

#### Definition of women of childbearing potential

Woman of childbearing potential (WOCBP) is defined as any female who have not undergone sterilization and are able to become pregnant anatomically and physiologically after menarche and before menopause.

Women without childbearing potential are defined as postmenopausal women or premenopausal women who have undergone sterilization procedure.

Postmenopause is defined as menopause for  $\geq 12$  months without alternative medical treatment.

Sterilization procedures include bilateral tubal ligation or bilateral oophorectomy or hysterectomy.

#### Requirements for contraception

In the whole study period and up to 6 months after the last dose of the investigational product, subjects and their partners must agree to one of the following operations:

- Complete abstinence of subjects and their partners. Periodic abstinence (e.g., calendar, ovulation, symptothermal or post-ovulation methods) is not allowed; or
- Correct use of one of the contraceptive methods with a failure rate of  $< 1\%$ :
  - Intrauterine device or intrauterine hormone-releasing system with an annual failure rate of  $< 1\%$  for subjects or their partners;
  - Vasoligation for subjects or their partners;
  - Subjects use double barrier method: Condoms and/or occlusion caps (diaphragm or cervical cap/dome cap), spermicide (foam/gel/film/cream/suppository) barrier method should be used as supplementary measures.

## 17.2 Appendix II: Calculation of Ccr

Ccr as calculated using the Cockcroft-Gault formula:

Ccr (mL/min) = (140-age (year)) × weight (kg)/72 × serum creatinine (mg/dL) ( $\times$  0.85, for female)

Ccr (mL/min) = (140-age (year)) × weight (kg)/0.814 × serum creatinine ( $\mu$ mol/L) ( $\times$  0.85, for female)

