## 4 Selection and Withdrawal of Subjects

### 4.1 Inclusion Criteria

Subjects who meet all of the following criteria will be eligible for this study:

1. Subjects who voluntarily participate in the clinical trial, and have signed the informed consent form (ICF), are able to understand and follow the study protocol, willing to visit the study site on time, fully understand the content, process and potential adverse reactions of the study, and indicate the date of signing the ICF;
2. Males or females aged 30-80 years (both inclusive) at the time of signing the ICF;
3. Subjects who are diagnosed with PD according to the Diagnostic Criteria for Parkinson's Disease in China (2016 edition);
4. The scores of modified Hoehn and Yahr Scale at screening are 1-2.5 (both inclusive);
5. Subjects who have not previously received anti-PD drugs; or those who have previously used any anti-PD drugs but have not received such drug within 4 weeks before study entry; or those who have received the anti-PD drug at a stable dose for at least 4 weeks before study entry and agree to maintain the original treatment regimen during the study;
6. Subjects with the scores of MDS-UPDRS Part III of  $\geq 22$  at screening (it should be scored  $\geq 12$  hours apart from the most recent dose of the anti-PD drug for subjects who have been receiving an anti-PD drug at a stable dose for at least 4 weeks prior to study entry);
7. Subjects of childbearing potential (including spouses of male subjects) who have no childbearing or sperm donation plan from the end of the screening period to within 6 months after the last dose and are willing to use at least one effective method (see [Appendix I](#) for details) for contraception.

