### 4.2 Exclusion Criteria

Subjects who meet any of the following criteria will be excluded from this study:

1. Presence of any medical condition that may interfere with full participation in the study, including but not limited to the following: medical history of epilepsy or any complications, medical history of hemolytic anemia, pulmonary embolism, respiratory depression, active psychiatric disease, or malignancy; positive tumor marker detection results at screening and judged by the investigator to be clinically significant;
2. Subjects who have experienced a New York Heart Association (NYHA) Class III or above congestive heart failure, unstable angina pectoris, acute myocardial infarction,

hemorrhagic stroke (stroke), and ischemic stroke (including transient ischemic attack) within 6 months before screening; or those who have undergone any percutaneous coronary intervention or coronary artery bypass grafting, heart valve repair/replacement; or those with severe arrhythmia as judged by the investigator at the time of screening;

3. Subjects with prior personal or family history of long-QT syndrome, family history of sudden death of any immediate family members (meaning a parent, child, or sibling) prior to the age of 40 years; and/or personal history of unexplained syncope within 1 year prior to screening; and/or QTcF > 450 ms (male), QTcF > 470 ms (female) measured by ECG at rest during screening;
4. Subjects with unstably controlled hypertension at screening, defined as the systolic blood pressure  $\geq 160$  mmHg and/or the diastolic blood pressure  $\geq 100$  mmHg (verify before randomization);
5. Subjects with symptomatic orthostatic hypotension at screening, or who experiences a decrease in systolic blood pressure of  $\geq 30$  mmHg or a decrease in diastolic blood pressure of  $\geq 15$  mmHg within 3 minutes when changing from the supine to the standing position (verify before randomization);
6. Atypical PD (e.g., Parkinsonism, multiple system atrophy, progressive supranuclear palsy), or secondary PD (e.g., delayed or drug-induced PD);
7. Subjects who have clinically significant hepatic insufficiency which is defined as the total bilirubin (TBIL)  $> 2 \times$  upper limit of normal (ULN) or alanine aminotransferase (ALT) and/or aspartate aminotransferase (AST)  $> 2 \times$  ULN;
8. Subjects who have clinically significant renal insufficiency (creatinine clearance [Ccr]  $< 30$  mL/min, see the calculation formula in [Appendix II](#));

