Hematology, blood chemistry, urinalysis, and coagulation tests are performed at all on-site visits in this study; creatinine clearance (Ccr) is calculated at visits V1, V2, V3, V6, and the early termination visit (if applicable) based on body weight measurements and serum creatinine levels from the blood chemistry tests, with the calculation formula provided in [Appendix II](#). (If body weight was measured during demographic data collection at V1, remeasurement is not required during that visit.) If hematology, blood chemistry, coagulation function test, urinalysis body weight measurement and Ccr calculation have been performed within 7 days (exclusive) before V2, these tests are not required to be repeated on V2; otherwise, they are required to be re-tested at V2 and the eligibility for the study enrollment should be confirmed according to the test results.

Although the screening for infectious diseases also requires laboratory tests, it is not a relevant parameter for the evaluation of the endpoint of this study. It should only be tested during the screening period; therefore, it is not listed in this section. Screening for infectious diseases is detailed in [Section 8.4](#).

Laboratory tests that require subjects to be fasted are provided in [Section 8.5](#).

If certain items are not included in routine tests at some study sites, they can be tested separately.

Information on sample collection, processing, preservation and destruction should comply with the regulations of the laboratory of the study site.

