3.3.2. Laboratory Tests

Including hematology, blood biochemistry, urinalysis, coagulation function, serum pregnancy test, urine pregnancy test, etc. The laboratory tests collected in the eCRF are listed in Table 1.

Table 1 Laboratory Test Items

Items	Examination Indicators
Hematology (CBC)	White blood cell count, absolute neutrophil count, neutrophil percentage, absolute lymphocyte count, lymphocyte percentage, absolute monocyte count, monocyte percentage, absolute eosinophil count, eosinophil percentage, absolute basophil count, basophil percentage, red blood cell count, hemoglobin, hematocrit, mean corpuscular volume, mean corpuscular hemoglobin, mean corpuscular hemoglobin concentration, red cell distribution width, platelet count, mean platelet volume, plateletcrit, and platelet distribution width
Blood Biochemistry	Fasting blood glucose, bile acid, total protein, albumin, globulin, albumin/globulin ratio, TBIL, direct bilirubin, indirect bilirubin, ALT, AST, γ -glutamyl transferase, alkaline phosphatase, lactate dehydrogenase, creatine kinase, creatine kinase-MB, urea/urea nitrogen, serum uric acid, creatinine, potassium, sodium, chloride, calcium, magnesium, inorganic phosphorus, triglycerides, total cholesterol, high-density lipoprotein cholesterol, and low-density lipoprotein cholesterol.
Creatinine clearance rate (Ccr)	Calculate Ccr based on body weight measurements and serum creatinine levels in blood biochemistry tests.
Urinalysis	Glucose urine, bilirubin urine, urine ketone body, urine pH, protein urine, urine urobilinogen, nitrite urine, occult blood urine, white blood cells urine, red blood cells urine, microscopic examination of urine sediment (red blood cells, white blood cells), and specific gravity urine.
Coagulation function	Prothrombin time, activated partial thromboplastin time, thrombin time, international normalized ratio, and fibrinogen
Pregnancy Test	Serum pregnancy and urine pregnancy

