6.12.3. Laboratory Tests

Descriptive statistics will be performed for the results of hematology, blood biochemistry, coagulation function, and Ccr measurements at each visit, as well as their changes from baseline.

For the clinical significance assessment of hematology, blood biochemistry, urinalysis, and coagulation function, cross-tabulation will be used to summarize the changes in subjects' clinical assessment categories from baseline to the worst post-baseline clinical assessment category (clinically significant abnormality > abnormality without clinical significance > normal > not examined). Analyze the "urine white blood cells" and "urine sediment microscopic white blood cells" results in the clinical significance of urinalysis collectively, and analyze the "urine red blood cells" and "urine sediment microscopic red blood cells" results collectively.

List the hematology, blood biochemistry, urinalysis, coagulation function, and Ccr of the subjects. Tabulate all abnormal test results.

For laboratory tests, if the original result contains an equal sign(e.g., \leq , \geq), the numeric value will be directly used. If the original result contains only a less-than symbol, subtract 0.0001 from the numeric value. If the original result contains only a greater-than symbol, add 0.0001 to the numeric value.

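### Appendix II prints the Cockcroft-Gault formula without brackets around the denominator; coded as printed, creatinine would multiply Ccr instead of dividing it

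*Protocol*

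**What the plan says.** Protocol Appendix II (17.2) introduces the calculation with "Ccr as calculated using the Cockcroft-Gault formula" and gives one line per creatinine unit. The mg/dL line contains "weight (kg)/72 × serum creatinine (mg/dL" and the µmol/L line contains "weight (kg)/0.814 × serum creatinine". Neither line brackets the product after the slash. A factor of 0.85 for women follows in parentheses at the end of each line.

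Three parts of the plan rely on this appendix:

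- **Eligibility.** Exclusion criterion 8 (Protocol 4.2) bars patients with Ccr below 30 mL/min and refers to Appendix II for the calculation.
- **Visits.** Protocol 8.2.4 says that Ccr "is calculated at visits V1, V2, V3, V6, and the early termination visit (if applicable", again with a reference to the appendix. Note 11 of the Schedule of Activities makes the same reference.
- **Safety tables.** SAP 3.3.2 (Table 1) says only "Calculate Ccr based on body weight measurements and serum creatinine levels in blood biochemistry tests". SAP 6.12.3 then plans "Descriptive statistics will be performed for the results of hematology, blood biochemistry, coagulation function, and Ccr measurements at each visit", with changes from baseline. The SAP does not print a formula.

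**The concern.** Multiplication and division have equal rank and are read from left to right. As printed, the quotient of weight and the constant is therefore multiplied by creatinine, and calculated Ccr rises as creatinine rises. That is the opposite of how a clearance estimate behaves.

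Appendix II is the only formula in either document, and the SAP does not correct it. Protocol 2.5.1 names renal toxicity (basophilic lesions in renal tubules) among the main toxicities. Creatinine is measured in local laboratories (Protocol 8.6) at about 7 sites, and the documents describe no central Ccr calculation. If a site spreadsheet or an edit check followed the mg/dL line literally, it could admit patients whom criterion 8 is meant to exclude, and exclude some with good renal function. It would also show falling renal function as rising Ccr.

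**Working it through.** **Inputs.** Constants 72 and 0.814, the term 140 − age, and the factor 0.85 come from Protocol Appendix II. The 30 mL/min limit comes from Protocol 4.2. Age 70 lies within the 30–80 years of Protocol 4.1. The weight of 60 kg is the one used in the dose justification (Protocol 5.2.2). The creatinine values are assumed for illustration. The unit conversion is also an assumption: 1 mg/dL = 88.4 µmol/L, from a molar mass of about 113.12. The documents give no worked Ccr value to reproduce.

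**Step 1: which reading makes the two lines agree?**

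- Ratio of the constants: 72 / 0.814 = 88.45, close to the unit conversion of 88.4.
- Creatinine as divisor: µmol/L line over mg/dL line = 72 / (0.814 × 88.4) = 1.0006. The lines agree to 0.06%.
- Creatinine as multiplier: ratio = (72 / 0.814) × 88.4 ≈ 7,819. The lines contradict each other for the same patient.

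So the appendix is consistent with itself only if creatinine is in the denominator.

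**Step 2: one patient under both readings.** Man aged 70, 60 kg, creatinine 2.5 mg/dL (221.0 µmol/L). (140 − 70) × 60 = 4,200.

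| Line | Bracketed | Literal |
|---|---|---|
| mg/dL | 4,200 / (72 × 2.5) = 23.3 | 4,200 / 72 × 2.5 = 145.8 |
| µmol/L | 4,200 / (0.814 × 221.0) ≈ 23.3 | 4,200 / 0.814 × 221.0 ≈ 1,140,000 |

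The bracketed form puts him below 30 mL/min. Either literal line puts him above it.

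**Step 3: where criterion 8 would bite** (same age and weight; 4,200 / 72 = 58.33).

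- Bracketed: Ccr < 30 when creatinine exceeds 58.33 / 30 = 1.94 mg/dL.
- Literal, mg/dL: Ccr < 30 when creatinine is below 30 / 58.33 = 0.51 mg/dL. The criterion is reversed.
- Literal, µmol/L: Ccr < 30 only when creatinine is below 30 × 0.814 / 4,200 ≈ 0.006 µmol/L. The criterion never applies; it is disabled, not reversed.

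**Step 4: direction of change.** If creatinine doubles from 1.0 to 2.0 mg/dL, the bracketed Ccr falls from 58.3 to 29.2 mL/min. The literal mg/dL line rises from 58.3 to 116.7. At 1.0 mg/dL the two readings coincide, so a spot check near that value would not detect the error.

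**Step 5: the factor for women.** A reader who repairs the line by taking everything after the slash as denominator could also divide by 0.85. For a woman aged 70, 60 kg, 1.8 mg/dL (assumed): 4,200 / (72 × 1.8) = 32.4. Multiplying by 0.85 gives 27.5; dividing by it gives 38.1. The parenthesis makes this slip less likely, but the new brackets should rule it out.

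**The case against.** The strongest reply is that the method is specified by name. Appendix II says Cockcroft-Gault, and Step 1 shows that its own constants disclose the intended form. A trained programmer would code it correctly, and no computed value in either document is wrong. This stands, and it is why the point is one of notation.

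A reader might infer that the renal exclusion and the Ccr tables in this trial are in fact inverted. The documents do not support that. The SAP prints no formula, and its dataset specifications are separate files (SAP 10.2) that are not available here. The creatinine unit reported by the local laboratories is not stated. Inversion of the exclusion would also need the mg/dL line; the µmol/L line would produce values that nobody could accept.

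The protocol has safeguards too. Serum creatinine itself is measured at site visits, apart from a limited waiver at V2. Investigators must mark out-of-range results and judge their clinical significance (Protocol 9.4.1.2). SAP 6.12.3 tabulates blood biochemistry beside Ccr, with shift tables of clinical significance. Ccr rising in step with creatinine should be visible there. These safeguards make undetected harm unlikely, but they do not correct the formula on which eligibility is calculated.

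Finally, a stacked fraction on the typeset page would carry its own grouping, which plain text loses. The inline slash on both lines makes this unlikely, but it cannot be fully excluded; a look at the page settles it.

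**Conclusion.** Both lines of Appendix II lack brackets around the denominator and, taken literally, are wrong. The consequence is conditional on someone coding the literal order. In mg/dL the results would be plausible but wrong (145.8 instead of 23.3 mL/min in the example), reversing exclusion criterion 8 and the direction of Ccr change. In µmol/L they would be impossible (over 1,000,000 mL/min) and would exclude nobody.

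The example patients are assumed, and no frequency of affected patients can be derived. Ccr is summarised descriptively and does not enter the primary endpoint, the estimand or any efficacy model. Severity is low. The correction is still worth making, because this is the only formula given for an eligibility criterion and a renal safety variable. The 30 mL/min threshold is not in question.

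**What to change.** In Protocol Appendix II, print:

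- Ccr (mL/min) = [(140 − age) × weight in kg] / (72 × creatinine in mg/dL)
- Ccr (mL/min) = [(140 − age) × weight in kg] / (0.814 × creatinine in µmol/L)
- For women, multiply the whole result by 0.85.

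Repeat this formula, with the unit, in SAP 3.3.2 or in the programming specification. Check the EDC derivation and any Ccr values already calculated at sites against it, using test cases away from 1.0 mg/dL.

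The cost is a few characters in the appendix, one line in the SAP or specification, and one verification check. No design element or planned analysis changes.
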